morbidity. Both projects demonstrated success in reducing asthma morbidity as measured by ED visits and hospitalizations.⁵⁻⁷ Long-term results over a 4 year period from the Allies Against Asthma Initiative found that policy and system changes continued as coalitions established routine care for each child.⁸ Sites within each project that were able to effect change in child asthma care highlighted the importance of strong coalitions and partnerships within communities. An example from Boston Children's Hospital, the Community Asthma Initiative (CAI), began with a needs assessment and developed a program of care around each child that provided asthma education, case management, home visits to assess asthma control and risk, home environmental assessment, and community outreach.⁹ Cost-benefit analyses of the CAI found a net present value of \$215,100 in gains for society, taking into account savings from fewer ED visits, hospitalizations, and missed school/work days.¹⁰ Reports from the CAI highlight the need to develop an Asthma Care Implementation Program (ACIP) that supports families with respect to culture, language, and beliefs through interventions in the home, school, and community.¹¹

B2 Rationale for this Study

Currently, however, there is no well-integrated, comprehensive, sustainable program of care for children with asthma in Richmond City. Richmond, an urban center, has been named as the Asthma Capital by the Asthma and Allergy Foundation (i.e., most challenging place to live in the United States with asthma) multiple times in the last five years. Richmond's asthma hospitalization rate is the highest of any locality in Virginia. An asthma care program is critical to reducing poor asthma outcomes in this high-risk group of children.

B3 COVID-19 Pandemic

In early 2020, RVA Breathes was impacted by the Coronavirus disease 2019 (COVID-19). COVID-19 is a respiratory illness caused by a virus called SARS-CoV-2. For the health and safety of staff and families, in-person interactions between research team and families were limited beginning March 13, 2020. Additionally, schools were closed and transitioned to remote instruction in mid-March. Thus, this protocol describes procedures both pre-COVID-19 (before March 13, 2020) with 217 families, and procedures after COVID-19 began with the remaining families enrolled in RVA Breathes. Changes to procedures due to COVID-19 are noted following original procedures.

C Study Objectives

C1 Primary Aim

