To evaluate a randomized control trial (RCT) of RVA Breathes.

- Conditions will be compared on the primary outcome of healthcare utilization (e.g., a composite of the frequency of asthma-specific ED visits and hospital admissions).
- Conditions will be compared on the secondary outcomes of school absences and medication usage.
- We hypothesize that children in the two active interventions will achieve greater reductions in healthcare utilization and school absences, and increases in controller medication usage at post-treatment and follow-up than children in the comparator condition.
- We will also *explore* differences in outcomes between the two active intervention conditions. This will provide important data for determining best practices in subsequent iterations of RVA Breathes.

C2 Secondary Aims

a) To evaluate the effectiveness of the RCT on secondary outcomes including asthma control, symptoms, and quality of life (QOL).

- We hypothesize that secondary outcomes of children in the intervention groups will be superior to those of the control group.

b) To identify putative mediators and moderators (e.g., caregiver asthma self-management skills, perceived stress, and depressive symptoms) of treatment outcomes.

- We hypothesize that intervention effects will be mitigated in families with caregivers with lower levels of asthma self-management skills at baseline, as well as in those with higher baseline levels of stress and depressive symptoms.

C3 Rationale for the Selection of Outcome Measures

[figure not shown]
Outcome measures were informed by the Social-Ecological Model and Interactive Systems Framework and drawn from recommendations by the Asthma Outcomes Steering Committee.

C4 Rationale and Risk/Benefits

Given that pediatric asthma disparities are a serious public health problem, the significance of this research project is high. As the study risks are small, the benefit to society outweighs subject risk. New information learned from this intervention study has the potential to improve the health and lives of urban children with asthma, as well as their families.

D Study Design

D1 Overview of Study Design

D2 Subject Selection and Withdraw

2.a Inclusion Criteria

Children and their caregivers must meet all of the inclusion criteria in order to be eligible to participate in the study:

- Child between the ages of 5 and 11
- Physician diagnosed asthma in child

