- To baseline/follow-up session questionnaires: “How has COVID-19 impacted your family?,” “How has COVID-19 impacted your child’s asthma care?,” “What has it been like not being able to access your child’s school nurse for asthma care?”

Change in school nurse intervention due to COVID-19: Per RPS protocol, school nurses will be contacting all students with a health condition at least once over the phone during the fall semester. This will include RVA Breathes participants. When a school nurse speaks with an RVA Breathes family, the school nurse will complete a modified data form that has been adapted for a non-clinic setting. This interaction could happen at any time throughout 2020.

E4 Baseline Session

Two RAs will attend the baseline session, which will last about 90 minutes. Caregivers will be compensated \$30 for their time and children will be given a parent-approved prize. At this visit, RAs will:

- Obtain and document consent from subject on study consent form, as well as child assent. This includes parental consent for their own participation and their child's participation.
- Verify inclusion/exclusion criteria.
- Administer the following measures:
 - Caregivers will report on family demographic information including caregiver and child's race/ethnicity, age, sex, monthly family income, education level, information on family structure, and their relationship to child.
 - Caregivers will report on the duration and number of times the child has been hospitalized due to asthma or visited the ED because of asthma in the last 12 months. This information will be verified by hospitalization and ED visit information from insurance companies and health systems.
 - Caregivers will report on the number of times their child missed school due to asthma in the last 12 months. This information will be verified by absentee data from the child's school.
 - Caregivers will report on the child's asthma medication name, dose, and refill information. We will also collect pharmacy refill data.
 - Caregivers and children will complete the Childhood Asthma Control Test (cACT) jointly, which measures the frequency of daytime and nighttime asthma symptoms, activity limitations, and perception of disease control.
 - Caregivers will report on number of symptom free days in the last 14 days on the Asthma Assessment Form.
 - Children will complete the Pediatric Asthma Quality of Life Questionnaire (PAQLQ).

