 - Caregivers will complete the Pediatric Asthma Caregiver Quality of Life Questionnaire (PACQLQ) and report on their own quality of life.
 - Caregivers will complete the Asthma Self-Efficacy Management Questionnaire (ASMQ), Perceived Stress Scale (PSS), Centers for Epidemiologic Studies Depression Scale (CES-D), and Stressful Life Events and Conditions Checklist (SLECC).
- Complete a brief semi-structured interview with the parent and child. Questions will ascertain:
 - Family satisfaction with the intervention sessions
 - Whether they would recommend the program to a friend
 - Perceived usefulness of the interventions
 - What behavioral changes they made because of the program
 - Changes they have seen in their child’s daily asthma symptoms (if any)

Changes due to COVID-19:

- Session occurs over the phone or via video (see Section E3)
- Question added to packet
 - How has COVID-19 impacted your family?,” “How has COVID-19 impacted your child’s asthma care?,” “What has it been like not being able to access your child’s school nurse for asthma care?”
- Payment occurs via contactless payment drop-off (see Section E3) or via e-gift card.

E11 3-month follow-up

Two RAs will complete the 3-month follow-up session in the family’s home. Caregivers will be compensated \$70 for their time and children will be given a parent-approved prize. At this visit, RAs will:

- Administer the following measures:
 - Caregivers will report on the duration and number of times the child has been hospitalized due to asthma or visited the ED because of asthma since the post-intervention session. This information will be verified by hospitalization and ED visit information from insurance companies and health systems.

- Caregivers will report on the number of times their child missed school due to asthma in the last 3 months. This information will be verified by absentee data from the child's school.
- Caregivers will report on the child's asthma medication name, dose, and refill information. We will also collect pharmacy refill data.
- Caregivers and children will complete the Childhood Asthma Control Test (cACT) jointly, which measures the frequency of daytime and nighttime asthma symptoms, activity limitations, and perception of disease control.
- Caregivers will report on number of symptom free days in the last 14 days on the Asthma Assessment Form.
- Children will complete the Pediatric Asthma Quality of Life Questionnaire (PAQLQ).

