- Session occurs over the phone or via video (see Section E3)
- Question added to packet
 - How has COVID-19 impacted your family?,” “How has COVID-19 impacted your child’s asthma care?,” “What has it been like not being able to access your child’s school nurse for asthma care?”
- Payment occurs via contactless payment drop-off (see Section E3) or via e-gift card.

E13 9-month follow-up

Two RAs will complete the 9-month follow-up session in the family's home. Caregivers will be compensated \$100 for their time and children will be given a parent-approved prize. At this visit, RAs will:

- Administer the following measures:
 - Caregivers will report on the duration and number of times the child has been hospitalized due to asthma or visited the ED because of asthma in the last 6 months. This information will be verified by hospitalization and ED visit information from insurance companies and health systems.
 - Caregivers will report on the number of times their child missed school due to asthma in the last 6 months. This information will be verified by absentee data from the child's school.
 - Caregivers will report on the child's asthma medication name, dose, and refill information. We will also collect pharmacy refill data.
 - Caregivers and children will complete the Childhood Asthma Control Test (cACT) jointly, which measures the frequency of daytime and nighttime asthma symptoms, activity limitations, and perception of disease control.
 - Caregivers will report on number of symptom free days in the last 14 days on the Asthma Assessment Form.
 - Children will complete the Pediatric Asthma Quality of Life Questionnaire (PAQLQ).
 - Caregivers will complete the Pediatric Asthma Caregiver Quality of Life Questionnaire (PACQLQ) and report on their own quality of life.
 - Caregivers will complete the Asthma Self-Efficacy Management Questionnaire (ASMQ), Perceived Stress Scale (PSS), Centers for Epidemiologic Studies Depression Scale (CES-D), and Stressful Life Events and Conditions Checklist (SLECC).

Changes due to COVID-19:

- Session occurs over the phone or via video (see Section E3)
- Question added to packet
 - How has COVID-19 impacted your family?,” “How has COVID-19 impacted your child’s asthma care?,” “What has it been like not being able to access your child’s school nurse for asthma care?”
- Payment occurs via contactless payment drop-off (see Section E3) or via e-gift card.

E14 Metrics from CHWs, Healthy Homes, and PCPs

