Aim 1: We hypothesize that children in the two active interventions will achieve reductions in healthcare utilization (e.g., asthma-specific ED visits, hospital admissions) and school absences, and an increase in controller medication use (calculated from refill data from insurers) at post-treatment and follow-up than children in the comparator condition. Our primary outcome, healthcare utilization, will be defined as a composite of the frequency of asthma-related inpatient and ED visits. A composite variable (i.e., sum score) that takes into account the frequency of asthma-related inpatient and frequency of ED visits will be calculated for each participant. At baseline, historical data will be obtained to ensure that we have captured utilization for the 9 months prior to the baseline visit (i.e., utilization before the intervention begins). Our primary endpoint is the change in mean rate of ED/hospitalization in 9 months before to 9 months after RVA Breathes across groups. Generalized Linear Mixed Models (GLMM) will be used to determine within person changes in healthcare utilization across time, and then differences in healthcare utilization between groups (e.g., intervention vs. control). Thus, our main outcome is change in healthcare utilization at the individual level as an average of individuals. We will also *explore* differences in outcomes between the two active intervention conditions [(1) asthma education + home remediation + school intervention vs. 2) asthma education + home remediation] to determine the value of adding a school-based component. Differences in healthcare utilization (and other outcomes) will again be tested using a Generalized Linear Mixed Model (GLMM). GLMM models will be fit to multiple types of dependent variables including, Gaussian/Normal, Binomial, Poisson and Negative Binomial. The GLMM model fit will include a between-subject factor (Group, representing the control group and the two intervention groups) and will also include a random effect for the cluster (school). These models will be modified in longitudinal assessments by the inclusion of a within-subject factor (Time [pre, post]) and the interaction between Group and Time variables. The inclusion of the interaction terms allows for a formal test of differing courses between the groups over time. To account for seasonality and the impact of COVID-19, we will include sine and cosine functions of $x = 2\pi \cdot (\text{time} / \text{max(time)})$ covariates and COVID-19 impact as covariate in analyses. COVID-19 impact will be designated as March 13, 2020 and Covariate=0 for months before COVID-19 and Covariate=1 for months after COVID-19. We will adjust for multiple comparisons using the Holm-Bonferroni method. In addition to healthcare utilization, we will also consider changes in the secondary outcomes of asthma action plans and controller medication use between conditions.

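### School absences are raw counts over windows of unequal length and unequal school days; analyse them per school day in session

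*Protocol*

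**What the plan says.** Protocol C1 makes absences part of the primary-aim hypothesis, as a secondary outcome: "children in the two active interventions will achieve greater reductions in healthcare utilization and school absences", compared with the comparator condition. The SAP repeats this under Aim 1, although its closing sentence on secondary outcomes there lists only asthma action plans and controller medication use.

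The recall windows are:

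- Baseline (E4) and post-intervention (E10): "Caregivers will report on the number of times their child missed school due to asthma in the last 12 months".
- 3-month (E11) and 6-month (E12) follow-up: "Caregivers will report on the number of times their child missed school due to asthma in the last 3 months".
- 9-month follow-up (E13): "Caregivers will report on the number of times their child missed school due to asthma in the last 6 months". This window overlaps the one used at the 6-month visit.

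At each visit the protocol adds: "This information will be verified by absentee data from the" child's school. The schedule in E2 also lists school attendance in the school nurse log. No count of days in session is mentioned.

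On the closure, protocol B3 says: "Additionally, schools were closed and transitioned to remote instruction in mid-March". It gives no reopening date, and neither document says whether a missed remote day is an absence.

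The SAP (Aim 1) applies its GLMM to the other outcomes as well as to utilization. The terms are Group, Time (pre, post), their interaction and a random school effect. No offset or exposure term is named. The calendar adjustments are one sine/cosine pair in 2π·time/max(time) and a step: "COVID-19 impact will be designated as March 13, 2020 and Covariate=0 for months before COVID-19 and Covariate=1 for months after COVID-19".

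**The concern.** A child can be absent only on a day when school is held. Three features of this trial make the number of such days vary widely between counts: the windows differ in length, a short window can fall mostly in summer or wholly in term depending on when the family enrolled, and schools left in-person teaching during the study.

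Without a denominator, a count of zero from a child who attended every day looks the same as a zero from a window with almost no school. The change that the model reads as an effect of time then mixes absence behaviour with opportunity. At stake are the readability of within-arm change, the precision of the between-arm comparison and, if enrolment timing differs by arm, its freedom from bias.

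**Working it through.** The documents give no absence rate, effect size or power for this outcome, so there is no stated figure to reproduce. They give no school calendar either; every school-day count below is an assumption.

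**1. School days per 3-month window.** Assume 180 days spread evenly over 9.5 months (September to mid-June): 180/9.5 = 18.95 a month, half of that in June, none in July or August. Totals by start month, January to December:

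57, 57, 57, 47, 28, 9, 19, 38, 57, 57, 57, 57

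The mean is 45, the coefficient of variation (CV) 0.366 and the range about 9 to 57. Three day-by-day calendars with other start and end dates and usual breaks (187 to 190 days a year) give minima of 8 to 12 and maxima of 63 to 65, a 5.4- to 7.9-fold range.

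**2. Longer windows.** Under those three calendars, 6-month windows hold 68–72 to 118 days (1.6- to 1.7-fold). Pre-closure 12-month windows hold 186 to 192 (ratio 1.0). Summer therefore does not distort a 12-month baseline compared with a 12-month post-intervention count when both precede the closure.

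**3. Twelve-month windows that span the closure.** On the 180-day calendar, count only in-person days up to March 13, 2020 and assume no reopening:

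| Window ends | In-person days | Share of 180 | Fall at constant daily risk |
|---|---|---|---|
| June 2020 | 122 | 68% | 32% |
| September 2020 | 103 | 57% | 43% |
| December 2020 | 46 | 25% | 75% |

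The three other calendars, with windows ending on the 13th of the month, give 29–33% for June and about 70% for December.

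**4. Do the SAP's covariates repair this?**

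- *Sine/cosine.* As written the period is max(time), which is annual only if max(time) is 12 months. A Poisson fit of school days on a correct annual pair explains 92–94% of the deviance for 6-month windows but only 49–52% for 3-month windows, where observed/fitted runs from 0.27 to 1.50.
- *COVID flag.* It is defined by month, but the response is a count over 3 to 12 months. A 12-month count ending in June 2020 has about 8.5 months before the switch and 3.5 after, so neither 0 nor 1 describes it. If both were coded 1, the windows ending June and December 2020 would share one coefficient while holding 122 and 46 in-person days (122/46 = 2.65).

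**5. Cost in noise.** For a Poisson count with mean μ, varying opportunity multiplies the variance by 1 + μ·CV². Assuming a mean of 2 absences in a 3-month window, season alone gives 1 + 2 × 0.366² = 1.27. This is before covariate adjustment, so it is an upper figure for the seasonal part.

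**6. Between-arm effect under no treatment effect.** Suppose an ordinary 3-month window holds 58 days and a low-school window 12. With 25% low windows in both arms the rate ratio is 1.00. With 35% against 25% it is (0.65 × 58 + 0.35 × 12)/(0.75 × 58 + 0.25 × 12) = 41.9/46.5 = 0.90. Varying the low window from 0 to 20 days gives 0.87 to 0.92; at 45% against 25% the range is 0.73 to 0.84. These shares are illustrations; the documents report none.

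**7. With an offset.** If log(days in session) is the offset and daily risk is constant, the null ratio is 1.00 for any window with at least one school day.

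**The case against.** The strongest reply is that the hypothesis is comparative. A closure shared by one district affects all arms, the Group-by-Time interaction compares concurrent groups, and schools are matched on demographics and location with block randomization (protocol 2.e). With similar calendar timing by arm, the null ratio is 1.00 without any offset. The SAP also does not ignore the calendar: its flag should absorb much of the contrast between windows wholly before and wholly after the closure, and a correct annual pair would serve 6-month windows well. Absences are secondary, and the sample size does not depend on them.

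Most of that stands, and it limits the point. It leaves the poor fit for 3-month windows, the undefined flag for windows that span the closure, and the added noise.

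Four stronger readings are tempting, and the documents do not support them:

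- *Every arm will show a fall made by the calendar.* Pre-closure 12-month windows are nearly equal. Families enrolled after March 2020 (83 if the planned 300 were reached, since 217 came under the earlier procedures) have closed or remote time in their baseline window, so their counts could rise.
- *The trial cannot tell whether the programme reduced absences.* That would need calendar timing to differ by arm. Allocation by school with recruitment partly through schools makes this possible, but nothing in the documents shows it.
- *A child with no school in the window is scored 0.* The plan does not say how such windows are coded, and remote instruction is not absence of school.
- *The closure more than doubles the variance.* Setting 30% of windows to zero in-person days gives CV 0.787 and 1 + 2 × 0.62 = 2.24. This ignores the COVID covariate and holds the mean at 2 after removing 30% of opportunity; with a mean of 1.4 the figure is 1.87, still unadjusted.

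**Conclusion.** The point holds in a limited form. Absences have no school-day denominator, and opportunity varies about 6-fold between 3-month windows on the 180-day calendar (5.4- to 7.9-fold on the others). A 12-month window ending in June 2020 loses about a third of its in-person days, and later ones lose more if schools stayed closed. The planned covariates correct this only partly.

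Raw within-arm change across unequal windows, or across the closure, should not be read as change in absence behaviour. Between arms the certain cost is noise; bias is conditional on timing. The sizes rest on assumed calendars, on counting only in-person days after March 13, 2020, and on no reopening within the windows. The absence of a denominator rests on the text alone. This is a worthwhile, inexpensive improvement to a secondary analysis and does not touch the primary endpoint.

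**What to change.** Define the outcome in the SAP as asthma absences per school day in session. For each child and window, derive the days in session while enrolled from the district calendar and school records, and enter its log as an offset in the Poisson or negative binomial GLMM. Set a window with zero school days to missing, not 0.

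Numerator and denominator must match. Either count remote days in both, with an indicator for the remote period, or restrict both to in-person days using dated school absentee records. An in-person denominator under a caregiver total that may include remote days would bias the rate upward in windows that span the closure. State the choice before analysis. Also say how the overlap between the 6- and 9-month windows is handled, so that the same absences are not counted twice.

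The cost is SAP wording and one derived exposure variable. School absentee data are already being obtained, but days in session per child would have to be added, and children who leave the district (protocol E3 continues remote follow-up of families who move out of state) would need another source or a missing value. Zero-day windows leave this analysis. Under the in-person option, that could remove much of the absence data of families enrolled after the closure, which favours counting remote days in both parts if school records allow.
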